2.1 OBJECTIVES AND SCIENTIFIC AIMS

Primary Objective:

- To compare objective response rate (ORR) during the first 2 years of treatment as determined by the investigator using Response Evaluation Criteria in Solid Tumors (RECIST) 1.1 criteria between patients receiving Nivolumab and SBRT to those receiving Nivolumab alone. The ORR is defined as the number of patients randomized to a given arm with a best overall response (BOR) of complete response (CR) or partial response (PR) in non-irradiated lesions during the first 96 weeks after treatment initiation divided by the total number of patients randomized to the given arm.

Secondary Objectives:

- To compare Overall Survival (OS) of Nivolumab and SBRT to Nivolumab alone.
- To compare Progression Free Survival (PFS) of Nivolumab and SBRT to Nivolumab alone.
- To compare duration of response (DOR) between the Nivolumab alone arm and Nivolumab + SBRT arm.
- To compare treatment-related Adverse Events (tr-AE) of Nivolumab and SBRT to Nivolumab alone using Common Terminology Criteria for Adverse Events version 4.0 (CTCAE v 4.0).
- To evaluate cancer-specific health related quality-of-life using the EORTC-QLQ C-30.

Exploratory Objectives:

- Evaluation of tumor tissue PDL1 expression via IHC and its correlation with response.
- Evaluate of peripheral blood mononuclear cell composition and its correlation with response
- Evaluation of soluble PD-1 and PD-L1 and its correlation to response.
- Evaluation of neo-antigen expression (optional) and its correlation to response.

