4.1 OVERVIEW OF STUDY DESIGN/INTERVENTION

4.2 Design

This is a randomized (1:1), open label Phase 2 screening trial in subjects ≥ 18 years old with metastatic HNSCC. Subjects will stratified based on viral status (p16+ OPC/EBER+ NPC vs others) and then randomized to either Nivolumab with interdigitated SBRT or Nivolumab alone.

Subjects must undergo screening evaluations to determine eligibility within 28 days prior to randomization.

Sixty (60) subjects will be randomized to one of the following arms:

- Arm 1: Nivolumab 3mg/kg IV every 2 weeks
- Arm 2:
 - Image Guided, Stereotactic Body Radiotherapy (27 Gy over 3 fractions given every other day) to a single lesion to start by study day 14 (study day 1 is day of first dose of Nivolumab).
 - Nivolumab 3mg/kg IV starting day 1 and then every 2 weeks thereafter.
- Treatment with Nivolumab will continue until progression or unacceptable toxicity.

Key Inclusion Criteria:

- 1) Males and females ≥ 18 years of age.
- 2) Eastern Cooperative Oncology Group (ECOG) performance status ≤ 2 .
- 3) Histologically confirmed metastatic HNSCC, including nasopharynx WHO Type I-III histologies; patients can have simultaneous loco-regional disease.
- 4) Subjects must have at least two lesions:
 - One lesion must be safely amenable to irradiation in the opinion of the treating radiation oncologist. This can be a lesion that was previously irradiated as long as prior radiation preceded projected first fraction of SBRT by at least 6 months.
 - At least one, not-to-be-irradiated lesion measurable by CT or MRI per RECIST 1.1 criteria.
- 5) Available formalin fixed, paraffin-embedded (FFPE) tumor tissue block with unstained slides of tumor sample obtained via excisional, incisional, or core needle biopsy from a loco-regionally recurrent or metastatic lesion; FFPE tumor tissue block with unstained slides from the primary disease is acceptable with approval of principal investigator.
- 6) Documentation of tumor viral status (p16 testing for oropharynx, EBER for nasopharynx). Tests done on primary tumor specimens at outside institutions are sufficient to meet this criterion.
- 7) Prior palliative or curative radiotherapy must be completed at least 14 days prior to randomization.

Key Exclusion Criteria:

- 1) Active brain metastases or leptomeningeal metastases are not allowed.
- 2) Non-squamous histologies are not allowed; an exception is made for WHO Type I-III nasopharynx histologies.

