11.0 TOXICITIES/SIDE EFFECTS

An adverse event is defined as any new untoward medical occurrence or worsening of a pre-existing medical condition in a clinical investigation subject administered study drug and that does not necessarily have a causal relationship with this treatment. An AE can therefore be any unfavorable or unintended sign, symptom, or disease temporally associated with the use of study drug/radiation or not considered related to the study drug/radiation. All AEs should be defined using the CTCAE v 4.0. All grade 1-5 adverse events should be reported and attributed.

The causal relationship to study drug is determined by the investigators and should be used to assess all AEs. The causal relationships are defined as follows:

- Related: there is a reasonable causal relationship between study drug/radiation administration and the AE.
- Not related: there is not a reasonable causal relationship between study drug/radiation administration and the AE.

The common understood meaning of “reasonable causal relationship” is that there is evidence to suggest a causal relationship.

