All tr-AEs will be tabulated and summarized. The cumulative incidence of all tr-AEs and Grade 3+ tr-AEs, etc., will be compared between the two arms by using Gray's test. For this analysis all randomized subjects who received at least one dose of study drug will be included.

The questions on the HRQOL will be scaled and scored using the recommended EORTC Quality of Life Group procedures. Raw scores will be transformed using a linear scale ranging from 0 to 100, with a higher score representing a higher level of functioning or a higher level of symptoms. Wilcoxon rank sum tests will be conducted to compare the scores across the two arms and longitudinal plots will be made to visually examine the pattern of change of scores at each specified time point. If appropriate, an exploratory linear mixed model will also be used to incorporate correlations among various time points, and include additional variables such as interaction between treatment and number of assessments, site of the primary tumor, baseline score, and performance status.

Because the toxicity of Nivolumab combined with SBRT is unclear, we will utilize an interim stopping rule for Arm 2 based on the first 20 randomized to this arm to protect later patients from unacceptably high toxicity rate. Using data from recently reported early phase trials of Nivolumab in NSCLC, we view 14% as an acceptable rate of acute (within 3 months of study initiation) \geq Grade 3 treatment-related adverse events; an unacceptable rate of acute \geq Grade 3 treatment-related adverse events is 30%. If more than 5 (e.g. 6 or more) of the first 20 patients experience an acute \geq Grade 3 treatment-related adverse event, the trial will be stopped early. If the true toxicity rate is 30%, the above boundary assures a 58% probability of stopping the trial at interim analysis; if the true toxicity rate is 40%, there is an 87% chance of stopping the trial early. If the true toxicity rate is 14%, the above boundary has only a 5% probability of stopping the trial early. Of note, for radiation dermatitis, only Grade 4 treatment-related adverse events will be included in the interim analysis.

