17.3 Serious Adverse Event (SAE) Reporting

An adverse event is considered serious if it results in ANY of the following outcomes:

- Death
- A life-threatening adverse event
- An adverse event that results in inpatient hospitalization or prolongation of existing hospitalization
- A persistent or significant incapacity or substantial disruption of the ability to conduct normal life functions
- A congenital anomaly/birth defect
- Important Medical Events (IME) that may not result in death, be life threatening, or require hospitalization may be considered serious when, based upon medical judgment, they may jeopardize the patient or subject and may require medical or surgical intervention to prevent one of the outcomes listed in this definition

Note: Hospital admission for a planned procedure/disease treatment is not considered an SAE.

Suspected transmission of an infectious agent via the study drug is an SAE.

Although pregnancy, overdose, cancer, and potential drug induced liver injury are not always serious by regulatory definition, these events must always be handled as an SAE.

Any component of a study endpoint that is considered related to the study therapy (radiation or Nivolumab) should be reported as an SAE.

SAE reporting is required as soon as the participant signs consent and is registered. SAE reporting is required for 30-days after the participant's last investigational treatment or intervention. Any events that occur after the 30-day period and that are at least possibly related to protocol treatment must be reported.

An SAE must be reported to the IRB/PB within 5 calendar days of the event. The IRB/PB requires a Clinical Research Database (CRDB) SAE report should be submitted electronically to the SAE Office as follows:

For IND/IDE trials: Reports that include a Grade 5 SAE should be sent to [contact]. All other reports should be sent to [contact].

The report should contain the following information:

Fields populated from Medidata:

- Subject's name (generate the report with only initials if it will be sent outside of MSK)
- Medical record number
- Disease/histology (if applicable)
- Protocol number and title

Data needing to be entered:

- The date the adverse event occurred
- The adverse event
- The grade of the event
- Relationship of the adverse event to the treatment (drug, device, or intervention)
- If the AE was expected
- The severity of the AE
- The intervention
- Detailed text that includes the following

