17.2.2 Non Serious Adverse Events

The collection of non-serious adverse events should begin at initiation of treatment. Non-serious AEs should be followed to resolution or stabilization, or reported as SAEs if they have become serious. Follow-up is also required for non-serious SAEs that cause interruption or discontinuation of study drug and for those present at the end of study treatment as appropriate. All identified nonserious AEs must be recorded and described on the nonserious AE page of the CRF.

All non-serious adverse events should be collected continuously during the treatment period and for a minimum of 100 days following the last dose of Nivolumab.

Laboratory Test Result Abnormalities

The following laboratory test results abnormalities should be captured as non-serious or serious AEs.

- Any laboratory test that is clinically significant or meets the definition of an SAE.
- Any laboratory test result abnormality that required the subject to have Nivolumab discontinued or interrupted.
- Any laboratory test result abnormality that required the subject to receive specific corrective therapy.

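### The only planned between-arm safety comparison uses events that unblinded investigators judge treatment-related, and no all-cause comparison by arm stands beside it

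*Combined protocol and SAP*

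**What the plan says.** All references are to the combined protocol and SAP.

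- **Objective (Section 2.1).** A secondary objective is "To compare treatment-related Adverse Events (tr-AE) of Nivolumab and SBRT to Nivolumab alone".
- **Test (Section 14.0, secondary objectives).** "The cumulative incidence of all tr-AEs and Grade 3+ tr-AEs, etc., will be compared between the two arms by using" Gray's test, in randomized subjects who received at least one dose of study drug. No significance level or competing event is named.
- **Blinding (Section 4.2, Design).** "This is a randomized (1:1), open label Phase 2 screening trial in subjects" aged 18 or over.
- **Attribution (Section 11.0).** "The causal relationship to study drug is determined by the investigators and should be used to assess all AEs". An event is related when "there is a reasonable causal relationship between study drug/radiation administration and the AE". No blinded or independent adjudication is described.
- **Capture (Section 11.0).** "All grade 1-5 adverse events should be reported and attributed".
- **Other safety summaries (Section 17.1, monitoring of data to ensure safety).** All patients' adverse events are to be listed and broken down by severity and causality. A comparison by arm is not mentioned.
- **Serious events (Section 17.3).** "SAE reporting is required for 30-days after" the last study treatment or intervention. Later events must be reported only if a link to treatment is at least possible.
- **Non-serious events (Section 17.2.2).** These are collected throughout treatment and "for a minimum of 100 days following the last dose of Nivolumab".
- **Related provisions.** Section 10.2 schedules a visit within 100 days of the last dose that includes an adverse event assessment. Section 17.2.1 sends serious events to the drug supplier whether or not they are related, and gives no end date.

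**The concern.** The protocol says the toxicity of the combination is unclear, and judging causality is hardest in that situation. The person deciding whether an event is related knows the arm. In Arm 2 there are two candidate causes, in Arm 1 only one. The same event, with the same true cause, could be called related in one arm and unrelated in the other. A comparison restricted to related events cannot separate a difference in toxicity from a difference in labelling. At stake is the reading of a named secondary objective. The primary analysis and sample size are not involved.

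The usual guard is to repeat the comparison on all events regardless of cause. The plan requires those events to be recorded but does not say they will be compared by arm. How complete they would be after day 30 is also unclear, because the reporting rules for serious and non-serious events differ.

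**Working it through.** **1. The plan's own safety figures.** The only safety calculation is the interim rule for Arm 2 in Section 14.0: stop if 6 or more of the first 20 patients have an acute Grade 3+ treatment-related event. With X ~ Binomial(20, p), P(X ≥ 6) is:

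| True rate p | Stated | Recomputed |
|---|---|---|
| 14% | 5% | 5.1% |
| 30% | 58% | 58.4% |
| 40% | 87% | 87.4% |

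The figures reproduce. They take the attributed rate to be the true rate.

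**2. Can differential attribution create a difference between arms?** Assumptions, not from the documents: a 40% all-cause rate in both arms, and 35% of events called related in Arm 1, so 0.40 × 0.35 = 14%. From the plan: n = 30 per arm. A fixed-time two-proportion test at two-sided 0.05 stands in for Gray's test:

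power = Φ{ [ |p2 − p1|√n − 1.96√(2p̄(1 − p̄)) ] / √( p1(1 − p1) + p2(1 − p2) ) }, where p̄ = (p1 + p2)/2.

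This counts only rejections towards more toxicity in Arm 2, which would be about 2.5% with no difference.

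| Called related in Arm 2 | Attributed rate in Arm 2 | Chance of declaring excess toxicity |
|---|---|---|
| 45% | 18% | 6.2% |
| 55% | 22% | 12.3% |
| 65% | 26% | 21.0% |
| 75% | 30% | 31.8% |

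**3. Can it hide one?** Take true related rates of 14% and 30%, the plan's acceptable and unacceptable rates. Power is 31.8% with correct attribution. It falls to 16.3% if 80% of the Arm 2 events are called related (0.30 × 0.80 = 24%), and to 6.2% if 60% are (18%).

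**4. The interim rule depends on the same judgement.** At a true rate of 30%, calling 90%, 80%, 70% or 50% of events related gives attributed rates of 27%, 24%, 21% and 15%. The stopping probability falls from 58.4% to 46.4%, 34.3%, 23.0% and 6.7%. In the other direction, take a true related rate of 14%. Suppose also that a share b of patients (20-40%) has an independent unrelated event, of which a fraction f (10-30%) is called related. The attributed rate is 1 − 0.86(1 − bf), or 15.7% to 24.3%, and the stopping probability rises from 5.1% to between 8.1% and 35.5%. The ranges for b and f are assumptions.

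**5. The reporting windows.**

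| Event on days 31-100 after last treatment | In the treatment-related test? | Capture |
|---|---|---|
| Serious, possibly related | Yes | Still reportable under Section 17.3 |
| Serious, judged unrelated | Never, whatever the window | Not required by Section 17.3; Sections 10.2, 11.0 and 17.2.1 point to capture but do not settle it |
| Non-serious, either attribution | If related | Collected under Section 17.2.2 (100 days counted from last nivolumab dose) |

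The second row is the gap. It touches an all-cause analysis and leaves the planned test unchanged.

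**The case against.** Several points weigh on the other side.

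- **SBRT toxicity is part of what should be measured.** This stands. Including radiation in the definition of related is correct, and an excess of genuine radiation effects in Arm 2 is a finding. Only misattribution is bias, and the documents hold no evidence of how much to expect.
- **All adverse events are already to be tabulated.** This stands in part. Section 17.1 plans a summary by severity and causality, so safety reporting as a whole is not confined to related events. It does not promise a comparison by arm.
- **An all-cause comparison can blur a real effect.** This stands. Patients with metastatic disease have many disease-related events, and with about 30 per arm these may dilute a true difference. The analysis should therefore be supportive and should not replace the planned one.
- **The 30- and 100-day windows.** A reader might infer that unrelated serious events stop being collected at day 30, and that this distorts the planned comparison. The documents support neither. Section 17.3 is a reporting rule and keeps possibly related events in scope. Sections 10.2, 11.0 and 17.2.1 point to continued capture. Deaths are followed in any case through survival contacts. What remains is an unreconciled inconsistency.
- **A size taken from the protocol's background.** Section 3.3.3 gives 49% of patients with any serious event and 11.5% with a drug-related one. The gap is 37.5 points, and relabelling 10-20% of it in one arm gives 3.75-7.5 points. A reader might take that as the expected bias. It is not: the rates come from nivolumab alone in other tumours, they concern serious events while Section 14.0 compares all and Grade 3+ related events, and the 10-20% is assumed. It is also about 1-2 patients in 30. The standard error of 11.5% versus 19% is √(0.115 × 0.885/30 + 0.19 × 0.81/30), about 9 points.

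**Conclusion.** The concern holds for attribution. The plan's only between-arm safety comparison depends on a causality judgement made by people who know the arm, with an extra attributable cause in Arm 2, and no all-cause comparison by arm shows whether the result survives without that judgement. It is worth correcting because the guard costs little. It is not an error that invalidates the plan.

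The size cannot be stated from the documents. The 6-32% false-signal range and the fall in power from 32% to 16% or 6% rest on assumed attribution shares, an assumed 40% all-cause rate in the false-signal case, and a fixed-time test in place of Gray's. They show that the effect can run in either direction and can matter with 30 per arm. They do not predict what will happen.

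The window mismatch is a separate and smaller point. It cannot bias the treatment-related test, and it matters only for the completeness of the all-cause analysis.

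**What to change.** 1. **Section 14.0.** In treated subjects, add the same cumulative-incidence comparison by arm for all-cause adverse events, all-cause Grade 3+ events and serious events. Report it beside the treatment-related result and label it supportive. State the competing events and the significance level for Gray's test in both analyses.
2. **Sections 10.2, 17.3, 17.2.1 and 17.2.2.** Reconcile these to one collection window for serious and non-serious events that does not depend on attribution, and state that such events enter the trial database. A window of 100 days would match Section 17.2.2.

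The cost is one extra table and a modest number of additional serious-event records from days 31-100. The all-cause table may dilute a real difference with disease-related events, which is why it should sit beside the planned comparison. Sample size, the primary analysis and the stated interim probabilities do not change.

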8.1.4 Patient Reported Outcome Assessment

- EORTC QLQ-C-30 must be completed before administration of first dose of Nivolumab.

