10.1.3 Outcomes Research Assessment

- EORTC QLQ-C-30: will be completed on or before Day 1 of treatment, and then, starting at week 8 (+/- 2 weeks), every 8 weeks (+/-2 weeks) for the first 48 weeks and every 12 weeks (+/- 2 weeks) until either week 96 or disease progression (whichever occurs first).

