12.2.6 Health-Related Quality of Life

The EORTC-QLQ-C-30 is one of the most commonly used QoL instruments in oncology studies and has been assessed in previous studies evaluating health related quality of life in patients with head and neck cancer. It is a 30 item instrument comprising six functional scales (physical functioning, cognitive functioning, emotional functioning, social functioning, role functioning, and global quality-of-life) as well as nine symptom scales (fatigue, pain, nausea/vomiting, dyspnea, insomnia, appetite loss, constipation, diarrhea, and financial difficulties). Except for overall health status and global quality of life items, responses for all items are 4-point categorical scales ranging from 1 (not at all) to 4 (very much). The overall health/quality of life responses are 7 point Likert scales.

The questions on the EORTC-QLQ-C30 will be scaled and scored using the recommended EORTC Quality of Life Group procedures. Raw scores will be transformed using a linear scale ranging from 0 to 100, with a higher score representing a higher level of functioning or a higher level of symptoms. Clinical significance will be defined as differences of at least 10 points (on a 0-100 scale). For example, a mean increase of ≥ 10 points on a functional scale would indicated a moderate improvement, whereas a mean decrease of ≥ 10 points would be interpreted as moderate worsening.

12.3 EXPLORATORY END POINTS:

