For the exploratory objectives, all lab measurements will be summarized and descriptive statistics will be provided. When correlation between lab measurements and treatment outcomes are of interest, Wilcoxon rank sum tests will be conducted to examine the difference between responders and non-responders within each arm. An exploratory multivariate logistic regression analysis to determine whether, once adjusted for relevant clinical covariates and treatment arm, tumor PD-L1 or serum immunophenotypic changes predict for response to Nivolumab.

To clarify we define population for the above analyses

- Randomized subjects for ORR analysis: all enrolled subjects who were randomized and provided at least 6 months of follow-up after treatment initiation. This is the dataset for the primary objective and irORR.
- All randomized subjects: all enrolled subjects who were randomized. This is the dataset for baseline demographics and time-to-event endpoints (PFS, OS).
- Treated subjects: all randomized subjects who received at least one dose of study drug. This is the dataset for safety evaluation. For instance, if a subject receives a single dose of Nivolumab but withdraws from study prior to the first dose of radiation, that subject will be considered treated.
- Biomarker Subjects: all randomized subjects with available biomarker data.
- PRO subjects: all subjects with available Patient Reported Outcomes (PRO) data.

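### The only firm between-arm comparison of quality of life has no stated baseline adjustment; the model that includes the required baseline score is exploratory and conditional

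*Combined protocol and SAP*

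**What the plan says.** Section 2.1 lists quality of life among the secondary objectives: "To evaluate cancer-specific health related quality-of-life using the EORTC-QLQ C-30". Section 12.2.6 describes six functional and nine symptom scales, each transformed to 0–100, and takes 10 points as the clinically significant difference.

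The baseline questionnaire is a requirement. Section 8.1.4 states: "EORTC QLQ-C-30 must be completed before administration of first dose of Nivolumab". Section 10.1.3 agrees: the form "will be completed on or before Day 1 of treatment, and then, starting at week 8". After week 8 it is repeated every 8 weeks to week 48 and then every 12 weeks, ending at week 96 or at progression, whichever is earlier.

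Section 14.0, under the secondary objectives, gives the analysis. The firm statement is "Wilcoxon rank sum tests will be conducted to compare the scores across the two arms", accompanied by longitudinal plots. The next sentence adds: "If appropriate, an exploratory linear mixed model will also be used to incorporate correlations among various time points". The further variables offered for that model are a treatment-by-assessment interaction and "site of the primary tumor, baseline score, and performance status". No criterion for when the model is appropriate is given. The analysis set, at the end of Section 14.0, is "PRO subjects: all subjects with available Patient Reported Outcomes (PRO) data".

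**The concern.** The plan requires a baseline score and recognises it as a useful covariate, but leaves it out of the only analysis it commits to. In a trial of 60 patients, with questionnaires stopping at progression, few patients will contribute at later visits, so precision matters. A comparison without the baseline score is noisier than it need be, and if the arms happen to differ at baseline, part of that gap stays in the follow-up difference.

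The score and the visit are also undefined. With 6 + 9 = 15 scales and ten scheduled post-baseline assessments (weeks 8, 16, 24, 32, 40, 48, 60, 72, 84 and 96), the wording would allow up to 15 × 10 = 150 Wilcoxon tests, none of them marked as the lead. A reader of the final report could not tell which result answers the objective.

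**Working it through.** **Inputs from the documents.** 60 patients randomized 1:1 (Section 14.0); a 10-point difference of interest (Section 12.2.6); a baseline required before the first dose (Sections 8.1.4 and 10.1.3).

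**Inputs assumed.** The documents give no SD, correlation, alpha or power for quality of life. Assumed here: SD 20 to 25; baseline-to-follow-up correlation r of 0.6 as the central value, with ranges shown; two-sided 0.05; and 20 patients per arm at a visit, to allow for attrition.

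**The plan's own figure.** The available n is set by the response-rate calculation: 15% versus 45%, one-sided 0.10, power 0.80. Without continuity correction, n = [1.2816 × √(2 × 0.30 × 0.70) + 0.8416 × √(0.15 × 0.85 + 0.45 × 0.55)]² / 0.30² = 20.1. With the correction, n = (20.1/4) × [1 + √(1 + 4/(20.1 × 0.30))]² = 26.4, so 27 per arm and 54 in total. Then 54/0.90 = 60. The stated size reproduces.

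**Precision at one visit.** Unadjusted SE = SD × √(2/n). The adjusted SE (analysis of covariance) multiplies this by √(1 − r²), which is 0.8 at r = 0.6. Half-width = 1.96 × SE. Power = Φ(10/SE − 1.96). For n = 20 per arm:

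| SD | Analysis | SE | 95% half-width | Power for 10 points |
|---|---|---|---|---|
| 20 | unadjusted | 6.32 | 12.4 | 35% |
| 20 | adjusted | 5.06 | 9.9 | 51% |
| 25 | unadjusted | 7.91 | 15.5 | 24% |
| 25 | adjusted | 6.32 | 12.4 | 35% |

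The unadjusted rows are for a difference in means. For the Wilcoxon test with normal scores (efficiency 3/π), power is slightly lower: 34% at SD 20 and 23.5% at SD 25.

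**Other correlations and sample sizes.** The variance factor 1 − r² is 0.91, 0.75 and 0.51 at r = 0.3, 0.5 and 0.7.
- 27 per arm, SD 20: power is about 0.44 for Wilcoxon, against 0.49, 0.56 and 0.73 with adjustment at those three correlations.
- 27 per arm, SD 25: 0.30 against 0.34, 0.40 and 0.54.
- 15 per arm, SD 20, r = 0.5: 0.27 against 0.35.

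**If the scores are changes from baseline.** The variance factor becomes 2(1 − r), which is 0.8 at r = 0.6. Power at 20 per arm is then 42% (SD 20) or 29% (SD 25), still below the adjusted 51% and 35%. Below r = 0.5 a change score is less precise than the raw score.

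**Baseline imbalance.** With 30 per arm the SE of the baseline difference is 20 × √(2/30) = 5.16 or 25 × √(2/30) = 6.45 points. A gap of 10 points or more then has probability 5.3% to 12.1% per scale. The expected carry-over into the follow-up difference is r × gap: 0.4 × 10 = 4 to 0.7 × 10 = 7 points. To shift the follow-up difference by a full 10 points the baseline gap must be 10/r, or 16.7 points at r = 0.6. That has probability 0.1% to 1.0%, and stays below 3% across r = 0.4 to 0.7.

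**Test level.** In 20,000 simulated trials per correlation, with 27 per arm and normal scores, the Wilcoxon test rejected a true null in 4.7% of trials at nominal 5%. Given a baseline imbalance above one SE, this rose to 6%, 8% and 12% at r = 0.3, 0.5 and 0.7. Given a smaller imbalance, it fell to 4%, 3% and 2%.

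**The case against.** The strongest reply is that adjustment is already planned. The sentence after the Wilcoxon test names a mixed model with the baseline score in it, so the dispute is about which of two analyses leads. That is correct, and a reader who inferred that the plan has no baseline-adjusted analysis would be wrong. What stands is that the adjusted model is exploratory and conditional, with no criterion for running it.

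A reader might also infer that chance imbalance will be mistaken for a treatment effect, or can by itself cross the 10-point threshold. The documents and the arithmetic do not support this. The test keeps its level over randomization; the error rate rises only given an imbalance already observed; and only a fraction r of a baseline gap carries over.

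Nor does the text say that the scores are raw. Section 12.2.6 illustrates its threshold with mean increases and decreases, which is the language of change. The fair statement is that the score is undefined. Likewise, a baseline for every patient is a requirement and not a guarantee, because the analysis set is whoever has data.

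Two further replies stand. Quality of life is to be evaluated, where the other secondary outcomes are to be compared, and it has no stated alpha or power; adjustment would still leave it underpowered. And the stop at progression affects both analyses: the mixed model uses earlier scores but assumes that later ones are missing at random.

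**Conclusion.** The point holds as a cheap improvement. The one firm between-arm analysis of a secondary objective states no baseline adjustment and leaves the score and visit undefined, although a baseline is required and an adjusted model is already named in the plan. The loss is one of precision: at 20 per arm and r = 0.6, adjustment cuts the half-width by a fifth and adds about 11 to 16 points of power (24% to 35% at SD 25; 35% to 51% at SD 20). It would also remove the 4 to 7 points expected to carry over from an observed 10-point baseline gap at r = 0.4 to 0.7.

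These sizes rest on the assumed SD, correlation, number per visit and two-sided 0.05. They also use a single-visit analysis of covariance with complete data as a stand-in for the mixed model. The Wilcoxon test is not invalid, and nothing here touches the primary response-rate analysis.

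**What to change.** In Section 14.0, make the repeated-measures mixed model the main quality-of-life analysis and drop the conditional wording. Fit post-baseline scores on baseline score, arm, visit, arm-by-visit and the viral-status stratum. The last is the randomization factor and is not among the variables now listed.

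Name one lead scale and visit in advance, for example global health status at week 8; that particular choice is for the trial team. Report the remaining scales and visits as supportive. Keep the Wilcoxon test as a sensitivity check, defined on change from baseline at the lead visit.

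The cost is SAP wording; no new data are needed. The downside is that the model treats scores missing after progression as missing at random. The retained Wilcoxon test does not check that assumption, so the SAP should state it as a limitation.
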